	22.1 Delegation of Responsibility	
23.	DATA HANDLING AND RECORD KEEPING	41
	 23.1 Study Personnel. 23.2 Pre-Study Documentation Requirements	41 41 41
24.		42
	24.1 Source Documents	42

	24.2 Monitoring Plan	42
	24.3 Audits	.42
25.	QUALITY CONTROL AND QUALITY ASSURANCE	. 42
26.	ETHICAL CONSIDERATIONS	. 43
27.	STUDY TERMINATION	. 43
28.	PUBLICATION POLICY	. 43
29.	REFERENCES	. 43
30.	APPENDIX A – 3M SKIN CONDITION ASSESSMENT TOOL MERGED WITH BEECKMAN ET 2015 CONSENSUS DOCUMENT: IAD SEVERITY CATEGORISATION TOOL	
31.	APPENDIX B - INSTRUCTIONS FOR USE OF 3M™ CAVILON™ ADVANCED SKIN PROTECTANT	49
32.	APPENDIX C – INSTRUCTIONS FOR USE OF 3M [™] CAVILON [™] NO RINSE SKIN CLEANSER #3380	
33.	APPENDIX D – MANUFACTURER'S INSTRUCTIONS FOR CONVATEC SENSI-CARE® PROTECTIVE BARRIER (PART NUMBER 325614)	54

1. Protocol Synopsis

Study Title Investigational Product & Regulatory Status:	Randomized, Controlled, Multi-Center Study Comparing the Safety and Efficacy of 3M [™] Cavilon [™] Advanced Skin Protectant, in the Management of Incontinence- associated Dermatitis, to a Commercially Available ConvaTec Sensi-Care® Protective Barrier 3M [™] Cavilon [™] Advanced Skin Protectant is a 510(k) cleared product. The comparative product is a commercialized product, ConvaTec Sensi-Care® Protective Barrier (part number 325614), a skin protectant paste with 15% zinc oxide.
Randomization	Subjects at each site will be randomized in a 1:1 ratio to either 3M [™] Cavilon [™] Advanced Skin Protectant or ConvaTec Sensi-Care® Protective Barrier using a computer generated randomization schedule.
Study Objective(s) & Hypothesis:	Objective(s): The primary objective of the study is to compare the safety and efficacy of 3M [™] Cavilon [™] Advanced Skin Protectant and to determine superiority compared to a commercially available moisture barrier paste (with 15% zinc oxide) in the management of severe, Category 2 IAD among subjects suffering from urinary and/or fecal incontinence. The outcomes will include time to healing, skin improvement, pain reduction, and avoidance of secondary complications such as infections and pressure ulcers. Hypothesis: 3M [™] Cavilon [™] Advanced Skin Protectant is superior to 15% zinc oxide products for protecting and managing severe Category 2 IAD-damaged skin. 3M [™] Cavilon [™] Advanced Skin Protectant can achieve this superiority performance with fewer applications and therefore improves IAD skin care protocol adherence and saves nursing time and materials.

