7.2 Secondary Efficacy Endpoints

Secondary efficacy endpoints in this study will include:

- Re-epithelialization to a Category 1 or lower. The patient may still have erythema at the site. Pain scores during incontinence management will be measured on a 0-10 Faces Pain Scale Visual Analog and will be analyzed only for those adult subjects who can report pain. Pain scores during incontinence management will be measured on the FLACC scale for pediatric patients.
- Efficacy in subjects who switch from the comparative product to Cavilon Advanced Skin Protectant after failure to completely heal on the comparative product.
- Prevention of IAD, as measured by either:
- Areas of the buttocks that were free of IAD and remained free of IAD throughout the intervention
- IAD scores in subjects whose IAD improved and who continued on Cavilon Advanced Skin Protectantt.
- $\circ~$ The proportion of subjects who have no progression of IAD, while still experiencing incontinence, will be estimated.
 - Patient Quality of Life (QoL) as measured by the EQ-5D-5L questionnaire will be analyzed by comparing the change from baseline in each of the domains. The changes from baseline will be compared using an analysis of variance with center, product, type of skin (denuded or not), and interactions as factors in the model.
 - Nursing time will be summarized for time and motion to be completed on 2 subjects at each participating study site (one patient in each arm of the study). Each subject will have time and motion measured during a fecal incontinence episode
 - Incontinence product use will be recorded during the study, and summarized for both product groups. Product utilization, such as estimated cost per application, frequency of application and days of treatment will be considered. The purpose of this analysis is to provide estimates of total IAD management cost for both regimens.
 - Prevention of complications such as fungal infections and or pressure ulcer development.
 - Environmental cleanliness of multi-use comparative product packaging.

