11.1 Investigational Product Group and Comparative Group

The following assessments will be completed 3 times per week (i.e. on dosing days M-W-F or T-Th-Sat, W-F or TH-Sat) for subjects enrolled:

• Perform Skin Cleansing

- o Use 3M[™] Cavilon[™] No-Rinse Skin Cleanser or warm tap water and soft cloths.
- Avoid rigorous scrubbing to minimize friction damage.
- Record pain score using Faces Pain Scale Visual Analog for adults or FLACC scale for pediatrics
- Time and Motion (Completed on one subject in each product group at each site)
 - $\circ\,$ This should be done after you have experience with applying both products. Preferably dose 2 or later
 - Document the time taken to cleanse the skin during a fecal incontinence episode
 - Document the amount of supplies needed to cleanse the skin, as well as the cleansing procedures employed
 - Record pain score using Faces Pain Scale Visual Analog for adults or FLACC scale for pediatrics during cleansing and at product application.

• Conduct Skin Assessment

- Complete a skin assessment of the following six zones for its color, presence of lesions, and skin loss.
 - Zone 1: Includes the anus and 2 inches surrounding anal opening plus: for males score the scrotal sac and females the labia majora.
 - Zone 2: Crease between buttocks, above the anal opening and 2-3 inches below natural waistline
 - Zone 3: Left buttock starts above fold between thigh and buttock and extends upward to 2-3 inches below natural waistline
 - Zone 4: Left Posterior and medial upper thighs
 - Zone 5: Right buttock starts above fold between thigh and buttock and extends upward to 2-3 inches below natural waistline
 - Zone 6: Right Posterior and medial upper thighs

- IAD score will be calculated using 3M's validated Skin Condition Assessment Tool (see Appendix A)
- Take Photographs
 - Position the subject appropriately in order to capture all 6 zones of the buttocks.
 - Take the photograph including the paper ruler in the picture.
 - o Download photographs immediately to the EDC system for review by CRA.
- Medications
 - o Review and record changes to current medications.
- Adverse Events
 - Assess and record adverse events. Immediately report any Serious Adverse Event. (Refer to Adverse Event CRF instructions).
- Incontinence Episodes Care and Tracking

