11.2 Final Study Visit

The subject's participation in this study is completed after 21-42 -days of follow-up or when the subject is discharged from the facility. At the final visit the following assessments will be completed:

- Medications
 - Review and record changes to current medications.
- Adverse Events
 - Assess and record adverse events. Immediately report any Serious Adverse Event. (Refer to Adverse Event CRF instructions).
- Perform Skin Cleansing and record pain score before and after cleansing
- Conduct Skin Assessment
- Take Photographs
- Administer Quality of Life questionnaire
- Healthcare Worker Ease of Use Survey
 - Complete end of study product Ease of Use survey
- Documentation
 - Complete and check all documentation.

Page 27 of 54 Status: Release Version: 7 Issue Date: 8/31/2016 12:19:02 PM

Page 28 of 54 Status: Release Version: 7 Issue Date: 8/31/2016 12:19:02 PM

Schedule of Events

Assessment	Screening/ Enrollment	D1 /23	D2 /24	D3 /25	D4 /26	D5 /27	D6 /28	D7 /29	D8 /30	D9 /31	D10 /32	D11 /33	D12 /34	D13 /35	D14 /36	D15 /37	D18 /38	D17 /39	D18 /40	D19 /41	D20 /42	D21 /43	End of Study/ D22/D44
Informed Consent	Х																						
Inclusion/Exclusion	Х																						
Urine Pregnancy Test	X																						
Demographics	X																						
IAD History & Current Product Use	х																						
Medications	Х	Х																					Х
Pressure Sore Risk Assessment	Х																						
Quality of Life questionnaire	x																						X
Skin Cleansing	X	Х	Х	Х	Х	Х	Х	Х	Х	Х	X	Х	Х	Х	Х	Х	Х	Х	Х	Х	Х	Х	Х
*Skin Cleansing – Timing & Product Use	х			X																			
Skin Assessment / IAD scoring	X	X		X		X			X		X		Х			X		X		X			X
Photographs	Х	Х		Х		Х			Х		X		Х			Х		Х		Х			Х
Sensi-Care Product Application Arm		х	X	X	Х	Х	X	X	X	Х	Х	Х	Х	Х	Х	Х	X	X	X	X	X		x
Cavilon Application		Х		Х		Х			Х		Х		Х			Х		Х		Х			
Clean Trace Assessment				X		Х			X		X		Х			Х		X		X			
*Product Application – Timing & Product Use				X																			
Healthcare Worker Ease of Use Survey		Х																					X
Incontinence Episode Care/Tracking		Х	X	X	Х	X	Х	Х	X	X	X	X	Х	Х	Х	X	X	X	X	X	Х	Х	X
Adverse Events		Х	Х	Х	Х	Х	Х	Х	Х	Х	Х	Х	Х	Х	Х	Х	Х	X	Х	Х	Х	Х	Х

* Only required for first Subjects in each product group

12. Subject Discontinuation

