19.1.3 Health Economics Analysis

The material used and nursing time spend to treat subjects with fecal or double incontinence over a three week (or shorter) period will be analyzed using an appropriate regression model. Detailed will be provided in the SAP.

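### A three-week regression of nursing time is planned, but time is measured for one post-treatment fecal episode in about 13 subjects per arm, under conflicting rules on whom to time

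*Combined protocol and SAP*

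**What the plan says.** **What is collected.** Section 7.2 calls for "time and motion to be completed on 2 subjects at each participating study site (one patient in each arm of the study") and continues: "Each subject will have time and motion measured during a fecal incontinence episode". Section 11.1 has the same restriction: "Time and Motion (Completed on one subject in each product group at each site"). Its text asks for the time taken to cleanse the skin and does not ask for application time. The Schedule of Events lists both: cleansing timing at Screening and Day 3, and application timing at Day 3.

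**Whom and when.** Three rules are given:
- Section 11.1: "This should be done after you have experience with applying both products. Preferably dose 2 or later".
- Schedule of Events footnote: "Only required for first Subjects in each product group".
- Section 19.1.1: a fecal episode after Dose 1, in a subset that is not defined.

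**What is analysed.** Sections 7.2 and 19.1.1 say only that nursing time will be summarized. Section 19.1.3 goes further: "The material used and nursing time spend to treat subjects with fecal or double incontinence over a three week (or shorter) period" is to be analysed with a regression model that is not named, with detail left to the SAP. The synopsis gives the same three-week analysis for subjects with urinary and/or fecal incontinence. The synopsis hypothesis says that the film "therefore improves IAD skin care protocol adherence and saves nursing time and materials".

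**The concern.** The regression needs a three-week nursing time for each subject, but the plan collects one post-treatment episode time in a small subset. With one such timing per subject, neither the variation between a subject's episodes nor any change in care time as the skin heals can be estimated. No urinary episode is timed, although the synopsis population includes subjects with urinary incontinence alone.

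The timing rules add a second problem. Sites that follow the footnote and sites that follow section 11.1 would time subjects at different levels of staff experience, and the data would be pooled as if collected under one rule.

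At stake is the saving of nursing time, which is part of the stated hypothesis and a listed secondary endpoint. A three-week figure could be read as measured when it is mostly assumed. The primary endpoint is not affected.

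**Working it through.** **1. The plan's own sample-size figure.** The only power statement (section 19.2) is for the primary endpoint: 51 per arm, difference 45, SD 70. Check: 45 / (70 × √(2/51)) = 45 / 13.86 = 3.25; 3.25 − 1.96 = 1.29; power ≈ 0.90. The stated power of at least 80% therefore holds. No SD, effect size or power is given for nursing time, so the results below are in SD units of the time per episode.

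**2. Number timed.** The synopsis expects at least 13 sites, with one subject per arm per site. That is 13 per arm, or 26 of 102 subjects (25.5%).

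**3. Precision per episode with 13 per arm.**
- Unpaired 95% half-width: t(24, 0.975) × √(2/13) = 2.064 × 0.392 = 0.81 SD.
- Paired by site: t(12, 0.975) × √(2(1 − ρ)/13). With ρ = 0.5: 2.179 × 0.277 = 0.60 SD. With ρ = 0.3: 2.179 × 0.328 = 0.72 SD. Both correlations are assumed, because the documents give none.

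| Timed per arm | 95% half-width, unpaired | Difference with 80% power, unpaired (t) | Paired, ρ = 0.3 | Paired, ρ = 0.5 |
|---|---|---|---|---|
| 13 | 0.81 SD | 1.15 SD | 1.00 SD | 0.85 SD |
| 15 | 0.75 SD | 1.06 SD | 0.92 SD | 0.78 SD |

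With 13 per arm unpaired, power for a 0.5 SD difference is 23%. Timing all 51 per arm would lower the difference with 80% power to (1.96 + 0.84) × √(2/51) ≈ 0.55 SD (normal approximation).

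**4. What a three-week total requires.** Section 13 logs cleansing episodes and product applications, so time per episode × count can be computed. Cleansing and application need different multipliers. The film is marked for 9 applications over 21 days in the Schedule of Events, while the paste goes on at every incontinence cleansing episode. Day 3, the only day marked for application timing, is a film application day. The documents give no episode rate, so assume 1, 3 or 8 per day over 21 days:

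| Episodes per day (assumed) | Episodes in 21 days | Film applications | Film applications wrongly charged if a combined Day 3 time is multiplied by all episodes |
|---|---|---|---|
| 1 | 21 | 9 | 12 |
| 3 | 63 | 9 | 54 |
| 8 | 168 | 9 | 159 |

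Multiplying by a count N also multiplies the uncertainty in the time by N. It adds no information about time per episode.

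**5. The timing rules side by side.** The schedule marks film application on Days 1 and 3, so Day 3 is dose 2. On the dose number, the schedule, section 11.1 and section 19.1.1 are compatible. They part on staff experience. A site's very first subject would normally reach Day 3 before staff had applied both products, so the footnote and section 11.1 would not both be met. The first subject in the other arm can meet both.

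**The case against.** A reader might infer several stronger points that the documents do not support.

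- **That no three-week analysis is possible.** Episodes and applications are counted, and the hypothesis ties the saving to fewer applications. An extrapolation is feasible; what is missing is a statement of its assumptions. The material-use part of section 19.1.3 does not depend on the timed subset at all.
- **That the new film is timed at first use, with a learning effect.** The schedule puts post-treatment timing at Day 3, which is dose 2, and section 19.1.1 says after Dose 1. No section asks for timing of the first film application, and section 17.2 provides product training. Limited experience at a site's first subject may remain, which is a smaller point.
- **That the first-subject footnote and section 11.1 can never both be met.** The conflict normally touches one of a site's two timed subjects, and the experience rule is worded as something that should be done.
- **That the regression will overstate precision.** No model is specified, so this cannot be shown.
- **That the endpoint is an underpowered test.** Sections 7.2 and 19.1.1 only summarize nursing time. The power figures show how little the data can resolve; they do not expose a failed power claim. Pairing by site and more than 13 sites would both improve precision.

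The synopsis also says, without a subset limit, that nursing time will be documented. Sections 7.2 and 11.1 and the schedule restrict the collection, so this adds an inconsistency and no data. Deferring the model to a SAP is legitimate, but a SAP cannot supply timings that were not collected.

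**Conclusion.** The concern holds as a mismatch between data and analysis, together with conflicting collection rules. A three-week nursing time is not observed. It can be obtained only by extrapolating from one post-treatment fecal episode in about 13 subjects per arm, on the unstated assumptions that time per episode is constant and that the timed subjects are representative. The half-width for a per-episode difference is about 0.81 SD unpaired, or 0.60 to 0.72 SD paired by site under assumed correlations of 0.5 to 0.3. A difference near 1 SD could still be detected; a moderate one probably would not. These sizes assume 13 sites that each time one subject per arm.

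The footnote and section 11.1 would normally conflict for a site's first subject, section 19.1.1 leaves the subset undefined, the synopsis and section 19.1.3 name different populations, and section 11.1 omits the application time that the schedule lists. These places need to be reconciled. The descriptive summary in sections 7.2 and 19.1.1 is sound as far as it goes.

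**What to change.** 1. In section 19.1.3 and the synopsis, limit the three-week regression to logged product and material use, in one stated population.
2. Report nursing time per fecal episode descriptively by arm, with the difference and its interval paired by site. Record cleansing and application time separately, and add application time to section 11.1. Make no three-week time-saving claim from these data.
3. If a three-week figure is kept, label it a model-based extrapolation and state the constant-time and representativeness assumptions. Multiply cleansing time by fecal cleansing episodes and application time by actual applications, and carry the timing uncertainty through.
4. Replace the schedule footnote with one rule consistent with section 11.1, and repeat it in sections 7.2 and 19.1.1: in each arm, the first subject with a fecal episode at dose 2 or later after site staff have applied both products. A rule based only on order within an arm, such as the second subject, would not ensure this, because a site's second film subject may enroll before any paste subject.

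The cost is wording in the protocol and SAP, one added timing field in section 11.1, and a weaker time-saving claim. Waiting for staff experience with both products may leave a site that enrolls few subjects without a timed pair.

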11.2 Final Study Visit

The subject's participation in this study is completed after 21-42 -days of follow-up or when the subject is discharged from the facility. At the final visit the following assessments will be completed:

- Medications
 - Review and record changes to current medications.
- Adverse Events
 - Assess and record adverse events. Immediately report any Serious Adverse Event. (Refer to Adverse Event CRF instructions).
- Perform Skin Cleansing and record pain score before and after cleansing
- Conduct Skin Assessment
- Take Photographs
- Administer Quality of Life questionnaire
- Healthcare Worker Ease of Use Survey
 - Complete end of study product Ease of Use survey
- Documentation
 - Complete and check all documentation.

Page 27 of 54 Status: Release Version: 7 Issue Date: 8/31/2016 12:19:02 PM

Page 28 of 54 Status: Release Version: 7 Issue Date: 8/31/2016 12:19:02 PM

Schedule of Events

Assessment	Screening/ Enrollment	D1 /23	D2 /24	D3 /25	D4 /26	D5 /27	D6 /28	D7 /29	D8 /30	D9 /31	D10 /32	D11 /33	D12 /34	D13 /35	D14 /36	D15 /37	D18 /38	D17 /39	D18 /40	D19 /41	D20 /42	D21 /43	End of Study/ D22/D44
Informed Consent	Х																						
Inclusion/Exclusion	Х																						
Urine Pregnancy Test	X																						
Demographics	X																						
IAD History & Current Product Use	х																						
Medications	Х	Х																					Х
Pressure Sore Risk Assessment	Х																						
Quality of Life questionnaire	x																						X
Skin Cleansing	X	Х	Х	Х	Х	Х	Х	Х	Х	Х	X	Х	Х	Х	Х	Х	Х	Х	Х	Х	Х	Х	Х
*Skin Cleansing – Timing & Product Use	х			X																			
Skin Assessment / IAD scoring	X	X		X		X			X		X		Х			X		X		X			X
Photographs	Х	Х		Х		Х			Х		X		Х			Х		Х		Х			Х
Sensi-Care Product Application Arm		х	X	X	Х	Х	X	X	X	Х	Х	Х	Х	Х	Х	Х	X	X	X	X	X		x
Cavilon Application		Х		Х		Х			Х		Х		Х			Х		Х		Х			
Clean Trace Assessment				X		Х			X		X		Х			Х		X		X			
*Product Application – Timing & Product Use				X																			
Healthcare Worker Ease of Use Survey		Х																					X
Incontinence Episode Care/Tracking		Х	X	X	Х	X	Х	Х	X	X	X	X	Х	Х	Х	X	X	X	X	X	Х	Х	X
Adverse Events		Х	Х	Х	Х	Х	Х	Х	Х	Х	Х	Х	Х	Х	Х	Х	Х	X	Х	Х	Х	Х	Х

* Only required for first Subjects in each product group

12. Subject Discontinuation

The Investigator may discontinue individual subjects from the study at any time. Subjects may voluntarily withdraw from the study at any time. The Investigator or study nurse will indicate on the appropriate CRF reason for, and date of, subject discontinuation.

Possible reasons for discontinuation are listed below:

- A subject develops a pressure ulcer in the sacral area (stage 3, 4, or unstageable, or any Deep Tissue Injury). The data from such a subject will be kept and analyzed to include the time during which the subject was in the study without a pressure ulcer.
- A subject develops a bacterial or fungal infection in the area included in the study or any other condition requiring the use of a topical treatment. Data collected up to the time where the subject required topical treatment will be analyzed.
- A subject develops any condition which, in the opinion of the Investigator, requires discontinuation from the study. If this condition is a suspected localized allergic reaction to the Cavilon Advanced Skin Protectant product, then appropriate testing confirmation should be performed and results/reports should be submitted to 3M. In addition, the event should be entered on the Adverse Event CRF.

The expectation is that subjects will be enrolled in this study for a period of 21 days. A subject who discontinues before the second IAD assessment, will be replaced with another qualified subject who will follow the same randomization scheme as the discontinued subject.

Subjects discontinued from the study will be returned to standard care and no further follow-up for this study will be performed.

13. Subject Compliance

Subject compliance is not an issue in this study as subjects will not be applying the product themselves. CRFs will be used to monitor the number of cleansing episodes, and number of product application(s), performed by skilled care givers.

14. Study Supplies

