6.4 Study Duration

In order to screen, enroll, and complete 102 evaluable subjects, an enrollment period of approximately 18-24 months is anticipated. Each adult subject may be followed for up to a maximum of 42 days or until the subject is discharged. Each pediatric subject may be followed for up to a maximum of 21 days or until the subject is discharged.

- 1. If the subject is discharged prior to 21 days, the subject will still have met the requirements for study completion.
- 2. Adult Subjects (>18years) can remain in the study for up to 21 days following enrollment receiving the Cavilon Advanced Skin Protectant or comparative product. All subjects will be discontinued at this point with the exception of the following 2 scenarios:
 - Subjects randomized to the comparative group, who fail to reach healing at the end of 21-day period with ongoing incontinence may be crossed over to the Cavilon Advanced Skin Protectant group and allowed to continue for up to an additional 21 days.
 - Subjects randomized to the Cavilon Advanced Skin Protectant group, who either re-epithelized or have a positive reduction in their IAD during the 21-day period, but remain hospitalized and continue to have incontinence, may continue to receive the Cavilon Advanced Skin Protectant product for up to an additional 21 days to evaluate prevention of IAD reoccurrence.
 - If a subject completely heals during the study, they may be discontinued at that time.
- 3. Pediatric Subjects Full term (37 weeks) to 18 years) can remain in the study for up to 21 days following enrollment receiving the Cavilon Advanced Skin Protectant product or comparative product. If the subject is discharged prior to 21 days, the subject will still have met the requirements for study completion.
 - Subjects randomized to the comparative group, who fail to improve (IAD) within 3 days of first application in the study may be crossed over to Cavilon Advanced Skin Protectant group and allowed to continue for up to an additional 21 days. The staff should cleanse the skin, complete skin assessments, and photographs prior to application of Cavilon Advanced Skin Protectant.
 - Subjects randomized to Cavilon Advanced Skin Protectant group, who fail to improve (IAD) within 3 days of first application in the study may be discontinued.

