16.3 Case Report Forms

3M intends to use electronic data capture (EDC) software for this study. Sites will be trained on the EDC software prior to study enrollment. Each site will be provided with a manual, including instructions on how to complete the electronic CRFs and how to make CRF corrections. Data may be recorded on data collection sheets prior to data entry into the EDC, or may be entered directly into the EDC system. Once the forms are completed, the monitor will review the CRFs to ensure accuracy and completeness. The Investigator must review and sign the CRFs for each subject in a timely fashion following completion. Data for this study will be entered on the CRFs:

CRF	Screening & Enrollment	Days 1-22 or early discharge	Days 23-42 or discharge	End of Study
Inclusion/Exclusion	x			
Subject History	x			
Medications	x	х	х	х
Braden Scale	x			
EQ-5D-5L Questionnaire	x		х	х
Incontinence Care		х	х	х
IAD History & Initial Skin Assessments	x			
3M Skin Assessment		x	х	x
Product Application		x	х	
Healthcare Worker Ease of Use Survey		x	х	x
Incontinence Episodes		x	х	x
Adverse Event		x	Х	x
Protocol Deviation		x	Х	x
Study Exit				х

17. Potential Risks and Benefits

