- Pain scores during incontinence management will be measured on a 0-10 scale, and will be analyzed only for those subjects from the ITT dataset who can report pain. This dataset will exclude those who are paraplegic or cannot respond. Infant pain will be measured with the FLACC tool⁴², and adults with the 0-10 Faces tool, and the data will be combined for statistical analysis. For this dataset, the pain scores will be compared by day using an analysis of variance with center, product, age group (infants vs adults), and interactions as factors in the model. If the age group-by-treatment interaction is significant (P<0.05), the data will be analyzed by age group. This response will be considered significant using a Hochberg's procedure for adjusting the P-values for this and the other secondary response of time to re-epithelialization.

- The proportion of subjects on each treatment group with stinging or burning upon application will be compared using a Cochran-Maentel-Haenzel test, stratifying for center.
- Percent change in IAD scores at each visit.
- Efficacy in subjects who switch from the comparative product to the investigational product after failure on the comparative product. For this analysis, the proportion of subjects with resolution of IAD as defined above will be estimated.
- Prevention of IAD in areas that had no denuded skin and remained free of IAD throughout the intervention. This will be estimated and tested using a Cox Proportional hazard model.
- Prevention of IAD, as measured by IAD scores in subjects whose IAD re-epithelialized and who continued on the investigational product. The proportion of subjects who have no progression of IAD, while still experiencing incontinence, will be estimated.
- Patient Quality of Life (QoL) as measured by the EQ-5D-5L questionnaire will be analyzed by comparing the change from baseline in each of the domains. The changes from baseline will be compared using an analysis of variance with center, product, type of skin (denuded or not), and interactions as factors in the model.
- Nursing time will be summarized for a fecal episode occurring post Dose 1 (after first treatment) for a subset of subjects. The nursing times will be summarized for both product groups.
- Incontinence product use will be recorded during the study, and summarized for both product groups. The purpose of this analysis is to provide estimates of total IAD management cost for both regimens.

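### EQ-5D-5L timing differs between section 11.2, the Schedule of Events and the CRF table, so an on-paste value is not assured for adults who switch and not planned for children who switch early; no rule says which value enters the between-arm comparison

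*Combined protocol and SAP*

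**What the plan says.** Four parts of the protocol bear on when EQ-5D-5L is taken and how it is used.

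- **Final visit (section 11.2).** The list includes "Administer Quality of Life questionnaire". On when that visit falls: "The subject's participation in this study is completed after 21-42 -days of follow-up", or at discharge from the facility. The on-treatment list in section 11.1 does not contain the questionnaire.
- **Schedule of Events (within section 11.2).** Columns overlay two periods (D1/23 up to D21/43). The questionnaire is marked at screening and then once more, in the column headed "End of Study/ D22/D44".
- **CRF table (section 16.3).** The row "EQ-5D-5L Questionnaire" is marked at screening, for Days 23-42 and at End of Study. It is blank for Days 1-22.
- **Analysis (section 19.1.1, repeated in 7.2).** "Patient Quality of Life (QoL) as measured by the EQ-5D-5L questionnaire will be analyzed by comparing the change from baseline in each of the domains". Product is among the factors of the analysis-of-variance model. No post-baseline visit is named and switchers are not mentioned.

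On switching, section 6.4 says that adults in the comparative group who have not healed by day 21 and are still incontinent "may be crossed over to the Cavilon Advanced Skin Protectant group and allowed to continue for up to an additional 21 days". Children in that group may switch if they fail to improve within 3 days. Section 11.1 lists what staff do before a switching child receives the film: cleansing, skin assessment and photographs. The questionnaire is not listed.

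**The concern.** A between-arm quality-of-life comparison needs a post-baseline value taken at a comparable time, and one whose treatment exposure is known. The IAD score has many assessments before any switch, so a pre-switch value exists. For EQ-5D-5L the three descriptions of timing do not agree. A site that follows section 11.2 and the CRF table would collect a switcher's only post-baseline value after a period on film.

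Two consequences follow. First, film-period quality of life can be counted in the paste arm. Second, subjects who stop at about day 22 are averaged with those who continue to about day 44, and continuation is selected in opposite directions: paste subjects continue because they did not heal, film subjects because they healed or improved (section 6.4). A questionnaire not given at the time cannot be collected later.

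**Working it through.** There is no planned quality-of-life effect, SD or power to reproduce. The only sizing figure is for the primary endpoint (section 19.2: 51 per arm, SD 70%, difference 45%, at least 80% power). As a check: 70 × √(2/51) = 13.86; 45/13.86 = 3.246; power = Φ(3.246 − 1.960) = 90.1% at two-sided 0.05. The statement is true as a lower bound, and nothing below depends on it.

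**Step 1: is there an on-paste value for a switcher?**

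| Source | Adult who switches after day 21 | Child who switches after day 3 |
|---|---|---|
| Section 11.2 text | Only at the final visit, on film | Only at the final visit, on film |
| CRF table, 16.3 | None in Days 1-22; Days 23-42 is on film | None in Days 1-22 |
| Schedule, D22 and D44 both meant | Yes, at D22 | No; D22 is about 22 − 3 = 19 days after the switch |
| Schedule, D22 or D44, whichever is the end | No | No |
| Pre-switch steps, 11.1 | Not described for adults | Questionnaire not listed |

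For adults, one reading of one source gives an on-paste value. For children, none does.

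**Step 2: which schedule reading is right?** Every other column pairs a first-period day with a second-period day, and the second period begins at D23. In the last column the row "Sensi-Care Product Application Arm" is marked and the film row is not, which suggests that D22 belongs to the first period. Against that, the CRF period containing day 22 is the one with no EQ-5D-5L, and section 11.2 ties the form to the final visit, which D22 is not for a subject who continues. The document does not settle it. Cell alignment in the extracted table is also uncertain.

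**Step 3: size if no on-paste value is taken.** Let D be the true film-minus-paste difference and s the share of the paste arm that switches. Assume that switchers fully reach the film level by their final questionnaire. The paste-arm mean then moves by sD towards film, so the observed difference is D − sD = (1 − s)D. With 51 per arm:

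| s (assumed) | Paste subjects with a final on-paste value, 51(1 − s) | Observed/true difference |
|---|---|---|
| 10% | 45.9 | 0.9 |
| 20% | 40.8 | 0.8 |
| 30% | 35.7 | 0.7 |
| 40% | 30.6 | 0.6 |
| 50% | 25.5 | 0.5 |

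The documents give neither s nor the degree of catch-up. With partial catch-up the loss is smaller. The effect of mixing day-22 and day-44 values cannot be sized from the documents.

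**Step 4: do existing rules cover it?** Section 19.4 carries the last observation forward for critical efficacy data such as healing time. For a switcher without a pre-switch form, the only earlier EQ-5D-5L value is baseline. Leaving switchers out removes paste subjects because they failed to heal or improve, so the remaining paste group is selected on outcome.

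**The case against.** The case on the other side has real force. A reader might infer three stronger things, and the documents do not support them.

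- *That EQ-5D-5L is taken only at screening and at the end.* The CRF table has a separate Days 23-42 entry, and the D22/D44 column can be read as two administrations.
- *That no switcher has a value on paste.* Adults can switch only after the 21-day period. If D22 is collected, it closes their time on paste.
- *That the comparison is beyond recovery.* With a D22 value, a simple rule gives the adult comparison. Without it, a comparison by randomised arm is still possible, though diluted, and non-switchers still have on-paste final values.

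Other points also stand. Many subjects may never reach a switch: discharge before day 21 counts as completion, only a 7-day expected stay is required, and switching is optional. Under full catch-up the bias is towards no difference, so it would not produce a false claim for the film. Quality of life is one of many secondary endpoints, and the Hochberg adjustment for secondary responses in section 19.1.1 names only pain and time to re-epithelialization. That section also leaves analytical detail to the SAP, where a visit rule could be stated.

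What remains is that an analysis rule cannot supply a form that was not given. The blank Days 1-22 cell fits poorly with a D22 questionnaire, and nothing provides one before an early pediatric switch.

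**Conclusion.** The point holds as an inconsistency in collection with an analysis gap attached. A pre-switch EQ-5D-5L value is not assured for adults who switch after day 21 and is not planned for children who switch after day 3. The comparison by product does not say which visit is used or how switchers are counted.

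The likely consequence is dilution and mixed timing, not loss of the comparison. The factor 1 − s applies only if a share s switches and fully catches up; both are assumptions, and the table of s values is an illustration, not an estimate. For a secondary endpoint this is a moderate matter, worth correcting because it is cheap and cannot be repaired afterwards. Whether newborns and subjects who cannot respond can be assessed with EQ-5D-5L is a separate, lesser question on which this conclusion does not rest.

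**What to change.** 1. Reconcile section 11.2, the Schedule of Events and the CRF table so that EQ-5D-5L is collected at D22 from every subject still in the study, before any second-period product is applied. Give D22 its own schedule column, separate from D44, and mark the form in the Days 1-22 CRF column.
2. Where a paste subject switches earlier, collect the form before film is first applied, with the skin assessment and photographs already required at that point.
3. State in section 19.1.1 and the SAP that the between-arm endpoint is the change from baseline to D22, or to the exit visit if earlier, analysed by randomised arm. Use pre-switch values for early pediatric switchers in a sensitivity analysis. Report values from Days 23-44 descriptively.

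This leaves some limits that should be stated. Early discharges still contribute values before D22, and the main analysis still includes film-period values from children who switched early, which is why the sensitivity analysis is needed. The cost is a few minutes per continuing or switching subject, at contacts that already take place, and small edits to the schedule, the CRF table and the analysis text.
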